5.8.5.5 Guidelines for Pneumonitis

Pneumonitis has been observed in subjects receiving trametinib. To reduce the risk of pneumonitis, subjects will be monitored closely for symptoms, evaluated with imaging and functional tests. Dose modification and supportive care guidelines for pneumonitis are described in [Table 17](#).

Table 17 Management and Dose Modification Guidelines for Pneumonitis

CTCAE Grade	Adverse Event Management	Action and Dose Modification
Grade 1	
 • CT scan (high-resolution with lung windows) recommended • Clinical evaluation and laboratory work-up for infection • Monitoring of oxygenation via pulse-oximetry recommended • Consultation of pulmonologist recommended 	
 • Continue trametinib at current dose
Grade 2	
 • CT scan (high-resolution with lung windows) • Clinical evaluation and laboratory work-up for infection • Consult pulmonologist • Pulmonary function tests –if < normal, repeat every 8 weeks until ≥ normal • Bronchoscopy with biopsy and/or BAL recommended • Symptomatic therapy including corticosteroids if clinically indicated 	
 • Interrupt trametinib until recovery to grade ≤1 • Restart with trametinib reduced by one dose level • Escalation to previous dose level after 4 weeks and consultation with Novartis Medical Lead possible • If no recovery to grade ≤1 within 4 weeks, permanently discontinue study treatment
Grade 3	
 • CT scan (high-resolution with lung windows) • Clinical evaluation and laboratory work-up for infection • Consult pulmonologist • Pulmonary function tests-if < normal, repeat every 8 weeks until ≥ normal • Bronchoscopy with biopsy and/or BAL if possible • Symptomatic therapy including corticosteroids as clinically indicated 	
 • Interrupt trametinib until recovery to grade ≤1 • After consultation with Novartis Medical Lead, study treatment may be restarted reduced by one dose level • If no recovery to grade ≤1 within 4 weeks, permanently discontinue study treatment
Grade 4	
 • Same as grade 3 	
 • Permanently discontinue study treatment or if recovers to grade ≤1 obtain Novartis Medical Lead approval if patients is expected to benefit from the study treatment

- BAL= broncioalveolar lavage; CT = computed tomography; CTCAE = Common Terminology Criteria for Adverse Events

5.9 Monitoring, Interruption and Stopping Criteria for Hepatobiliary Events

5.9.1 Liver Chemistry Stopping Criteria

These liver chemistry stopping and follow-up criteria have been designed to assure subject safety and evaluate liver event etiology in alignment with the FDA premarketing clinical liver safety guidance).

<http://www.fda.gov/downloads/Drugs/GuidanceComplianceRegulatoryInformation/Guidances/UCM174090>.

Liver chemistry stopping criteria 1-5 are defined below and an algorithm is presented in Appendix 6:

1. ALT $\geq 3xULN$ and bilirubin $\geq 2xULN$ ($>35\%$ direct bilirubin) (or ALT $\geq 3xULN$ and INR >1.5 , if INR measured)

NOTE: If serum bilirubin fractionation is not immediately available, study treatment should be discontinued if ALT $\geq 3xULN$ and bilirubin $\geq 2xULN$. Serum bilirubin fractionation should be performed if testing is available. If testing is unavailable, record presence of detectable urinary bilirubin on dipstick, indicating direct bilirubin elevations and suggesting liver injury.

2. ALT $\geq 8xULN$
3. ALT $\geq 5xULN$ but $<8xULN$ persists for ≥ 2 weeks
4. ALT $\geq 3xULN$ if associated with the appearance or worsening of symptoms believed to be hepatitis (such as fatigue, nausea, vomiting, right upper quadrant pain or tenderness, or jaundice) or hypersensitivity (such as fever, rash or eosinophilia).
5. $5xULN$ but $<8xULN$ and cannot be monitored weekly for >2 weeks.

When any of the liver chemistry stopping criteria 1 – 5 is met, do the following:

- **Immediately discontinue subject from study treatment**
- Report the event to Novartis **within 24 hours** of learning its occurrence
- Complete the liver event CRF and SAE data collection tool if the event also meets the criteria for an SAE
 - All events of ALT $\geq 3xULN$ **and** bilirubin $\geq 2xULN$ ($>35\%$ direct bilirubin) (or ALT $\geq 3xULN$ and INR >1.5 , if INR measured; INR measurement is not required and the threshold value stated will not apply to subjects receiving anticoagulants), termed ‘Hy’s Law’, **must be reported as an SAE**.
 - NOTE: if serum bilirubin fractionation is not immediately available, study treatment should be discontinued if ALT $\geq 3xULN$ **and** bilirubin $\geq 2xULN$. Serum bilirubin fractionation should be performed if testing is available. If testing is unavailable, **record presence of detectable urinary bilirubin on dipstick**, indicating direct bilirubin elevations and suggesting liver injury

- Complete the liver imaging and/or liver biopsy CRFs if these tests are performed
- Perform liver event follow up assessments, and monitor the subject until liver chemistries resolve, stabilize, or return to baseline values as described below
- Withdraw the subject from the study treatment after completion of the liver chemistry monitoring as described below (unless further safety follow up is required or Novartis Medical Governance approval of drug restart is granted, as described in Section 5.9.1.3).
 - Follow up for overall survival is required following discontinuation from study treatment.
- Do not rechallenge with study treatment unless written approval for drug restart is granted by Novartis Medical Governance (details for restarting investigational product are described in Section 5.9.1.3, whereupon the subject continues in the study after completion of the liver chemistry monitoring described in Section 5.9.1.2).
- Subjects meeting criterion 5 should be monitored as frequently as possible.

In addition, for subjects meeting liver stopping criterion 1:

- Make every reasonable attempt to have subjects return to clinic **within 24 hours** for repeat liver chemistries, liver event follow up assessments (refer to Section 5.9.1.1), and close monitoring
- A specialist or hepatology consultation is recommended
- Monitor subjects twice weekly until liver chemistries (ALT, AST, alkaline phosphatase, bilirubin) resolve, stabilize or return to within baseline values.

For subjects meeting any of the liver stopping criteria 2 – 5:

- Make every reasonable attempt to have subjects return to clinic **within 24-72 hrs** for repeat liver chemistries and liver event follow up assessments (refer to Section 5.9.1.1)
- Monitor subjects weekly until liver chemistries (ALT, AST, alkaline phosphatase, bilirubin) resolve, stabilize or return to within baseline values
- Subjects meeting criterion 5 should be monitored as frequently as possible.

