3.1 Study Design

Protocol waivers or exemptions are not allowed. Therefore, adherence to the study design requirements, including those specified in the Time and Events Table, are essential and required for study conduct.

This is an open-label, Phase IIA, multi-center study to evaluate the objective response rate of dabrafenib and trametinib combination therapy in subjects that have BRAF V600 mutation-positive ALM or cutaneous melanoma. Approximately 65 subjects will be enrolled to receive oral dabrafenib 150 mg twice daily in combination with oral trametinib 2 mg once daily.

Dose modification guidelines for adverse events are provided in Section 5.8. Other measures of efficacy including duration of response, PFS and OS, as well as PK and PD properties, safety and tolerability of dabrafenib and trametinib will also be evaluated. Blood and tissue samples will be collected to determine possible mechanisms of drug response and resistance. Subjects will continue study treatment until disease progression, death, unacceptable toxicity, withdrawal of consent, or study completion. After treatment discontinuation, subjects will be followed for survival and disease progression as applicable.

The study completion is defined as:

- In case all subjects stop study treatment within 48 weeks after Last Subject First Visit(LSFV): the study is completed once the last subject has completed the 48 weeks survival follow-up or all subjects die or loss to follow-up, whichever comes first.
- In case some subjects are still on study treatment 48 weeks after LSFV: the study is completed once all subjects stop study medication, or all subjects who are still on study medication can have access to alternative supply of MEK/BRAF inhibitors, whichever comes first.

Supplementary study conduct information not mandated to be present in this protocol is provided in the accompanying Study Procedures Manual (SPM). The SPM will provide the site personnel with administrative and detailed technical information that does not impact subject safety.

4 Subject selection and discontinuation/completion criteria

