5.9.1.2 Liver Chemistry Monitoring Criteria

For subjects with ALT ≥ 3 xULN **but** < 8 xULN which exhibit a decrease to ALT ≥ 3 xULN, but < 5 xULN **and** bilirubin < 2 xULN, without hepatitis symptoms or rash, and who can be monitored weekly for 4 weeks, the following actions should be taken:

- Notify the Novartis Medical Lead within 24 hours of learning of the abnormality to discuss subject safety
- Continue study treatment
- Return weekly for repeat liver chemistries (ALT, AST, alkaline phosphatase, bilirubin) until they resolve, stabilize or return to within baseline values
- If at any time the subject meets any of the liver chemistry stopping criteria 1 – 5, proceed as described above
- If, after 4 weeks of monitoring, ALT < 3 xULN and bilirubin < 2 xULN, monitor subjects twice monthly until liver chemistries normalize or return to within baseline values.
- Refer to Section 12.6 for an algorithm of liver chemistry monitoring, stopping, and follow-up criteria.

5.9.1.3 Drug Restart/Rechallenge Following Liver Events that are Possibly Related to Study Treatment

Approval by Novartis for study treatment restart can be considered where:

The subject is receiving compelling benefit, benefit of drug restart exceeds risk, and no effective alternative therapy is available. Ethics Committee or Institutional Review Board approval of study treatment restart/rechallenge must be obtained, as required.

If the restart/rechallenge is approved by Novartis in writing, the subject must be provided with a clear description of the possible benefits and risks of drug administration, including the possibility of recurrent, more severe liver injury or death.

The subject must also provide signed informed consent specifically for the study treatment restart/rechallenge. Documentation of informed consent must be recorded in the study chart. Study treatment must be administered at the dose specified by Novartis.

Subjects approved by Novartis for restart/rechallenge of study treatment must return to the clinic twice a week for liver chemistry tests until stable, liver chemistries have been demonstrated and then laboratory monitoring may resume as per protocol.

6 Concomitant Medications and Non-Drug Therapies

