6.2 Medications to be Used with Caution

The following medications should be used with caution as their concentrations may be altered by dabrafenib or they may alter dabrafenib concentrations:

- Drugs that are moderate inhibitors or inducers of CYP3A and CYP2C8 as they may alter concentrations of dabrafenib.
- Dabrafenib has been shown to induce CYP3A4 and CYP2C9 in vivo using midazolam (CYP3A4 substrate) and S-warfarin (CYP2C9 substrate). Dabrafenib is an in vitro inducer of CYP2B6 and other enzymes such as CYP2C8, CYP2C19, UDP-glucuronyl transferases. Transporters may also be affected. Co-administration of dabrafenib and medications which are affected by the induction of these enzymes (including warfarin) and transporters may result in loss of efficacy. If co-administration of these medications is necessary, investigators should monitor subjects for loss of efficacy or consider substitutions of these medications. A partial list of these medications is provided in the SPM.

- Therapeutic level dosing of warfarin can be used with approval by the Novartis Medical Lead and close monitoring of PT/INR by the site. Exposure decreased by 37% due to enzyme induction when on treatment, thus warfarin dosing may need to be adjusted based upon PT/INR. Consequently, when discontinuing dabrafenib, warfarin exposure may be increased and thus close monitoring via PT/INR and warfarin dose adjustments must be made as clinically appropriate. Prophylactic low dose warfarin may be given to maintain central catheter patency.
- Dabrafenib solubility is pH-dependent with decreased solubility at higher pH. Drugs such as proton pump inhibitors that inhibit gastric acid secretion to elevate gastric pH may decrease the solubility of dabrafenib and reduce its bioavailability. No clinical study has been conducted to evaluate the effect of pH on dabrafenib pharmacokinetics. In an ad-hoc analysis, no differences in the maximum peak concentration (C_{max}) and AUC were noted between subjects who reported taking pH-elevating products relative to other subjects. Due to the theoretical risk that pH-elevating agents may decrease oral bioavailability and exposure to dabrafenib, these medicinal products that increase gastric pH should be used with caution when administered with dabrafenib.

Table 19 Medications to be used with Caution

USE WITH CAUTION: : Moderate inhibitors of CYP3A, or CYP2C8 since concentrations of dabrafenib may be increased	

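### Liver stopping criterion 1 omits the anticoagulant exemption that the protocol attaches to the same INR test for SAE reporting

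*Protocol*

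**What the plan says.** Criterion 1 in Protocol 5.9.1 has two limbs. The first is ALT at least 3xULN with bilirubin at least 2xULN (more than 35% direct). The second is ALT at least 3xULN "and INR >1.5 , if INR measured". The note beneath it deals only with bilirubin fractionation. When any of criteria 1 to 5 is met, the first action is "Immediately discontinue subject from study treatment".

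Further down that action list, the bullet on Hy's Law SAEs repeats the ALT/INR test and adds that "INR measurement is not required and the threshold value stated will not apply to subjects receiving anticoagulants". The same exemption appears in 7.3.2.2 g (protocol-specific SAEs) and in note a to the reporting table in 7.3.10.

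Anticoagulated subjects are within the study population. Table 2, footnote b, lets them enrol with INR in the therapeutic range. Section 6.1 permits anticoagulants and recommends extra INR monitoring with warfarin. Section 6.2 states: "Therapeutic level dosing of warfarin can be used with approval by the Novartis Medical Lead and close monitoring of PT/INR by the site".

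Section 5.9.1.2 lets certain subjects with moderate ALT elevation continue under weekly monitoring, but gives way to the stopping rules: "If at any time the subject meets any of the liver chemistry stopping criteria".

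**The concern.** In a subject on warfarin, INR is raised by design and says little about liver synthetic function. The protocol accepts this three times for reporting, but the rule that ends treatment does not. A permitted background drug, rather than liver injury, could therefore trigger a stop.

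Without the INR limb, an asymptomatic subject with bilirubin below 2xULN stops only in one of three cases:

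- ALT reaches 8xULN (criterion 2).
- ALT of 5 to below 8xULN persists for two weeks (criterion 3).
- ALT is in that range and weekly monitoring is not possible (criterion 5).

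The INR limb lowers the bar to 3xULN. The stop is also hard to reverse. Section 5.9.1 says: "Do not rechallenge with study treatment unless written approval for drug restart is granted by Novartis Medical Governance". Section 5.9.1.3 adds: "The subject must also provide signed informed consent specifically for the study treatment restart/rechallenge". At stake is loss of effective therapy for an individual subject; the efficacy estimate is not at issue.

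**Working it through.** The plan gives no figure on this point, so the check is a comparison of text followed by a rough bound on size.

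**Where the ALT/INR test appears**

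| Place | Governs | Anticoagulant exemption |
|---|---|---|
| 5.9.1, criterion 1 | stopping treatment | no |
| 5.9.1, SAE bullet in the action list | SAE reporting | yes |
| 7.3.2.2 g | SAE definition | yes |
| 7.3.10, note a | prompt reporting | yes |

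The SAE bullet in 5.9.1 applies only once a stopping criterion has been met and discontinuation ordered. It therefore does not undo the stop.

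**Can the case arise?** It needs a measured INR. Table 22 schedules INR at screening only, while sections 6.1 and 6.2 call for INR monitoring on warfarin. On-treatment INR is thus most likely to exist in exactly the subjects for whom the protocol calls the threshold inapplicable.

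**Literal walk-through.** Take a subject on permitted warfarin with INR above 1.5, ALT that has fallen to between 3 and 5xULN, bilirubin below 2xULN, no symptoms or rash, and able to attend weekly.

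1. Section 5.9.1.2: continue treatment with weekly chemistry, unless one of criteria 1 to 5 is met.
2. Criterion 1: ALT is at least 3xULN and the measured INR exceeds 1.5, so the criterion is met and treatment stops.
3. Criteria 2 to 5: none is met.
4. SAE bullet and 7.3.2.2 g: the INR threshold is waived, so this is not a Hy's Law SAE.
5. Section 7.3.10: with the INR row set aside, the result falls in the mildest row, where the liver event form is not needed unless the elevation lasts two weeks or weekly monitoring is impossible.

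One laboratory result thus lands in the strictest stopping category and the lightest reporting category. With the exemption added to criterion 1, step 2 is not met and the subject continues under 5.9.1.2.

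**Size.** Inputs: 65 subjects (section 9.2.1) and ALT elevation reported as an AE in 11% on the combination (MEK115306, section 1.2.3).

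- Expected subjects with ALT elevation: 65 x 0.11 = 7.15.
- Share of these needed for one affected subject: 1 / 7.15 = 0.140, or 14%. They would have to be anticoagulated with INR above 1.5, reach 3xULN and meet no other stopping criterion. The documents give none of these shares.
- Assume 3% to 10% are anticoagulated with INR above 1.5, and set every other share at its ceiling of 100%: 7.15 x 0.03 = 0.21 and 7.15 x 0.10 = 0.72.

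The result is a ceiling for that assumed range. It takes the 11% to transfer to this population and anticoagulant use to be unrelated to ALT elevation. Not every ALT event reaches 3xULN. Many subjects would also meet criterion 4 through symptoms common on the combination (pyrexia 53%, nausea 35% in MEK116513, section 1.2.3). The true figure is therefore lower.

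**The case against.** The best defence is that 5.9.1 already contains the exemption a few lines below criterion 1, in a repeat of the same parenthesis. Since 1.5 is the only INR threshold in that section, an investigator may well read the exemption as general. That reading is available, but the clause sits inside the sentence defining what must be reported as an SAE, and a mandatory stop should not rest on inference. If the general reading is right, applying it is not a waiver. If it is not, a site that continues treatment meets section 3.1: "Protocol waivers or exemptions are not allowed".

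Second, the Appendix 6 algorithm is a figure not shown and may carry the exemption. That stands as a limit: the point is established for the text of 5.9.1 only. Even so, text and algorithm should agree.

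Third, stopping cautiously while not labelling the event a Hy's Law SAE could be deliberate. The protocol nowhere says so, and it treats the threshold as uninformative in these subjects wherever it addresses them.

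Fourth, section 6.2 reports a 37% fall in warfarin exposure through enzyme induction, which makes a high INR less likely. The same section expects the dose to be adjusted to PT/INR, so INR should be brought back to range.

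The remaining points stand. The sponsor's Medical Lead must approve therapeutic warfarin, and the sponsor is told of ALT rises within 24 hours, so a mistaken stop could be discussed quickly. The 3% to 10% share is an assumption. The case is rare, and the trial is finished.

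**Conclusion.** The concern holds as a minor inconsistency in a safety rule. As written, criterion 1 makes a permitted anticoagulant sufficient, together with ALT of 3xULN, to force discontinuation, while the protocol disapplies the same INR threshold in all three reporting provisions. Probably fewer than one of 65 subjects would be affected, and no reliable probability can be given. The conclusion requires a measured INR above 1.5. The protocol gives no therapeutic range, so it is an assumption that therapeutic dosing exceeds that value; prophylactic low-dose warfarin may not. It also rests on the text of 5.9.1, without sight of the Appendix 6 algorithm.

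**What to change.** Add one clause to criterion 1 in 5.9.1: *the INR limb is not applied to subjects on anticoagulants*. Confirm that the Appendix 6 algorithm says the same. Optionally, add a matching note to the INR item in the Appendix 7 restart checklist, where INR of 1.5 or more is a risk factor to be weighed and not a bar to restart. This would help because section 6.2 warns that warfarin exposure may rise once dabrafenib is stopped, so INR may climb further after the stop.

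No procedure is added. The cost is that INR no longer serves as a stopping signal for liver injury in anticoagulated subjects; the bilirubin limb of criterion 1 and criteria 2 to 5 still protect them. With last patient last visit on 19-Apr-2021 (SAP 2.1.1), the change can no longer help subjects in this trial and is mainly of use in protocols that reuse this liver text.

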5.9.1.1 Liver Event Follow-up Assessments

For subjects meeting any of the liver chemistry stopping criteria 1 – 5, make every attempt to carry out the **liver event follow up assessments** described below:

- Viral hepatitis serology including:
 - Hepatitis A IgM antibody
 - Hepatitis B surface antigen and Hepatitis B Core Antibody (IgM)
 - Hepatitis C RNA
 - Cytomegalovirus IgM antibody
 - Epstein-Barr viral capsid antigen IgM antibody (or if unavailable, obtain heterophile antibody or monospot testing)
 - Hepatitis E IgM antibody.
- Blood sample for pharmacokinetic (PK) analysis, obtained within 10 days of last dose. Record the date/time of the PK blood sample draw and the date/time of the last dose of study treatment prior to blood sample draw on the CRF. If the date or time of the last dose is unclear, provide the subject's best approximation. If the date/time of the last dose cannot be approximated OR a PK sample cannot be collected in the time period indicated above, do not obtain a PK sample. Instructions for sample handling and shipping are in the SPM. **PK sampling will be discontinued 8 weeks after last patient first treatment.**
- Serum creatine phosphokinase (CPK) and lactate dehydrogenase (LDH).
- Fractionate bilirubin, if total bilirubin $\geq 2xULN$.
- Obtain complete blood count with differential to assess eosinophilia.
- Record the appearance or worsening of clinical symptoms of hepatitis, or hypersensitivity, such as fatigue, nausea, vomiting, right upper quadrant pain or tenderness, pyrexia, rash or eosinophilia as relevant on the AE form. Please note that treatment with trametinib often associates with rash which is usually acneiform and affects the scalp, face, neck, chest, and upper back. Discuss with Novartis Medical Lead as needed.
- Record use of concomitant medications such as acetaminophen, herbal remedies, other over the counter medications, or putative hepatotoxins, on the concomitant medications form.
- Record alcohol use on the liver event alcohol intake form.

The following assessments are required for subjects with ALT $\geq 3xULN$ and bilirubin $\geq 2xULN$ ($>35\%$ direct) but are optional for other abnormal liver chemistries:

- Anti-nuclear antibody, anti-smooth muscle antibody, and Type 1 anti-liver kidney microsomal antibodies and quantitative total immunoglobulin G (IgG or gamma globulins).
- Liver imaging (ultrasound, magnetic resonance, or computerized tomography) to evaluate liver disease.

- Serum acetaminophen adduct assay (quantifies potential acetaminophen contribution to liver injury, in subjects with definite or likely acetaminophen use in the preceding week. **NOTE: not required in China** [James LP 2009].
- Only in those with underlying chronic hepatitis B at study entry (identified by positive hepatitis B surface antigen): quantitative hepatitis B DNA and hepatitis delta antibody. **NOTE:** if hepatitis delta antibody assay cannot be performed,, it can be replaced with a Polymerase chain reaction (PCR) of hepatitis D RNA virus (where needed) [Le Gal F 2005].

